1.0 OBJECTIVES

The overall goal of the Skin Cancer Prevention Program Project is to employ novel technologies and develop new therapeutic strategies to prevent intraepithelial neoplasias in the skin (i.e. actinic keratosis, cutaneous squamous cell carcinoma *in situ*). Our objectives in pursuit of this goal are to determine clinical, histopathologic, and protein/phosphoprotein signaling patterns associated with human skin carcinogenesis and to develop safe, highly efficacious intervention strategies for the prevention of skin cancer. The **overall hypothesis of the project** is that Toll-like Receptor 4 (TLR4) and T-LAK cell-originated protein kinase (TOPK) / p53-related protein kinase (PRPK) drive important signaling pathways, with potential synergism to prevent cutaneous squamous cell carcinoma (cSCC), and that TOPK/PRPK and TLR4 signaling pathways are modulated in the skin by acute exposure to solar simulated light (SSL).

The aim of this study is to assess TLR4 and TOPK/PRPK signaling in sun damaged (SD) human skin acutely exposed to solar simulated light (SSL). The purpose of this aim is to assess the effect of acute UV exposure on the signaling pathways of interest in order to validate the acute clinical model prior to intervention with small molecule inhibitors. Acute UV exposure will be evaluated in SD skin to determine the level of activation of the targeted pathways using reverse-phase protein array (LCM-RPPA) analysis and immunohistochemistry (IHC). This translational aim will prospectively analyze TLR4 and TOPK/PRPK signaling pathways activation by acute exposure of human subjects to SSL at twice the minimal erythema dose (MED) for each subject. We will evaluate the modulation of key proposed signaling pathways using RPPA and IHC in acutely irradiated human skin. We will also determine the optimal time points for evaluation of biomarker modulation.

Primary Endpoint: To assess TLR4 and TOPK signaling pathway activation levels pre- and post-SSL exposure in SD skin.

Exploratory Endpoint: To assess the correlation between SD level and the magnitude of SSL-induced pathway activation.

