Thirty-six (36) subjects with a broad range of SD on the forearm will be recruited. Based on the standardized clinical photodamage scale [1], we will include mild (N=12), moderate (N=12), and severely (N=12) sun damaged (SD) skin. The level of SD will be scored, using a range of 0-9, where absent SD = 0, mild SD = 1-3, moderate SD = 4-6 and severe SD = 7-9 (see Appendix C).

We will irradiate and biopsy the SD forearm skin of each healthy adult volunteer and collect skin punch biopsies before and after exposure to SSL for analysis using LCM-RPPA and IHC. The results of this study will be used to aid in design of pharmacodynamic SSL exposure studies with small molecule inhibitors in subsequent studies.

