5.0 PRE-STUDY REQUIREMENTS

Pre-study requirements include:

- Administration of the screening consent and HIPAA authorization form;
- Eligibility screening by a study medical provider, including a skin examination and a review of the subject's medical history, concomitant medications, and supplements;

- Subjects must have mild (N=12), moderate (N=12), or severe (N=12) sun damage [1] of the skin on the forearms (Appendix C).

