6.2 Trial Schema

Informed consent will be administered to all study participants. Female participants of childbearing potential will undergo a urine pregnancy test prior to SSL exposures. If there is a scheduling issue, a pregnancy test will be repeated if ≥ 7 days elapse between MED determination and the administration of SSL at 2X MED for biopsy. Each study participant will act as his/her own control. Areas to be used for baseline biopsies, MED (minimal erythema dose) determination, and study biopsy sites will be marked on the participant's skin with non-permanent surgical marking ink.

MED will be determined on the left buttock. After the MED of the subject is determined, three biopsy sites will be outlined on the left forearm. Then SSL at a dose of 2X MED will then be administered at two of the biopsy sites on the left forearm. Skin punch biopsies will then be collected at 1 hour (± 15 minutes) and 24 hours (± 2 hours) post-SSL exposure. In addition, one 6mm skin punch biopsy sample will be collected from the left forearm at baseline to serve as an unexposed (SSL) control sample. The control sample will be collected from a site that is at least 6 cm away from the sites exposed to SSL. All of the biopsy samples will be collected as close to the exact target time as possible. Photographs will be taken of the left forearm prior to skin punch biopsies. Study participants will return for suture removal and follow-up from 10 to 16 days after the final biopsies are collected, and they will be followed for as long as necessary if complications occur. Study participants may have their sutures removed by an outside provider per their preference.

Table 1 Outline of Trial Schema (n = 36)

Screening	Informed Consent Form and HIPAA authorization form administered; Skin examination and medical history reviewed by study provider
Visit 1*	Urine pregnancy test if necessary; SSL exposures administered for MED determination to left buttock.
Visit 2	MED visually determined
Visit 3*	Photograph of left forearm will be taken; SSL to 2 biopsy sites on left forearm at a dose of 2X MED; Biopsy collected from control biopsy site (no SSL) on left forearm; Biopsy collected from 1-hour test site on left forearm.
Visit 4	Photograph of left forearm will be taken; Skin biopsy collected from left forearm at 24 hours after SSL exposure
Visit 5**	Sutures removed 10-16 days after Visit 3

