8.0 STATISTICAL CONSIDERATIONS

8.1 Sample Size Determination

We will examine the TLR4 and TOPK signaling pathways in acute SSL-exposed SD human skin. Subjects with evidence of SD will be enrolled (N=36); with 85% expected to complete the study (30 evaluable subjects). Primary analysis will compare levels of RPPA analytes in each pathway as stated above in baseline unexposed samples vs. samples collected 1 or 24 h after SSL in SD skin. The power is 93% or above when the correlation between the \log_2 fold change of any two different analytes in the same pathway ranges from 0 to 0.4, and the power is 82% if the correlation is 0.6. Exploratory analyses will associate the SD score/severity level with analyte activation in the SD samples. Based on these analyses, the most appropriate post-SSL time point (per pathway) will be selected based on the combination with the largest effect sizes. Furthermore, an exploratory systems biology analysis will be conducted based on these analyses, one post-SSL time point (per pathway) will be selected for future studies based on the combination with the largest effect sizes. Furthermore, an exploratory systems biology analysis will be conducted.

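### Section 8.1 writes the primary SSL contrast without a sun-damage term; adding the fixed mild/moderate/severe strata to the log2 fold-change analysis would be a cheap, optional gain in power if activation differs by stratum

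*Combined protocol and SAP*

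**What the plan says.** Section 1.0 sets the sample by SD level: "we will include mild (N=12), moderate (N=12), and severely (N=12) sun damaged (SD) skin". Section 5.0 repeats it as an entry requirement: "Subjects must have mild (N=12), moderate (N=12), or severe (N=12) sun damage". The stratum sizes are therefore chosen by design.

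Section 6.2 makes the comparison within subject: "Each study participant will act as his/her own control". The control, 1 h and 24 h biopsies all come from the left forearm of the same person.

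Section 8.1 gives the primary analysis: "Primary analysis will compare levels of RPPA analytes in each pathway as stated above in baseline unexposed samples vs. samples collected" at the two post-exposure times. It names no test, model or covariate. Power is stated on the log2 scale and depends on how strongly analytes correlate. It is at least 93% where the correlation for "fold change of any two different analytes in the same pathway ranges from 0 to 0.4". At a correlation of 0.6 it falls to 82%.

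SD level appears only in exploratory work. Section 1.0 lists "Exploratory Endpoint: To assess the correlation between SD level and the magnitude of SSL-induced pathway activation", and section 8.1 has a matching exploratory analysis of SD score or severity against analyte activation.

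**The concern.** When stratum sizes are fixed in advance, differences between stratum means are not sampling error of the overall mean. A one-sample t test on the 30 fold changes, the most natural reading of section 8.1, still counts them as error. If SSL activation differs by SD level, that test's standard error is too large for the design, and power is lost that one extra factor would recover. The plan already records the stratum and already asks whether activation depends on it, so adjustment needs no new data.

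The stake is efficiency in a study whose estimated effects will guide the choice of time point for later trials. Type I error is not at risk.

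**Working it through.** **1. The plan's own figures.** Evaluable subjects: 36 × 0.85 = 30.6, which agrees with the stated 30. (Section 6.1 uses 80%, giving 36 × 0.80 = 28.8; the two rates should be reconciled.) The stated power cannot be reproduced, because alpha, sidedness, effect size, standard deviation, number of analytes and test are not given. A z test on the mean of m equally correlated analytes at n = 30 fits both 93% at correlation 0.4 and 82% at 0.6 with about 16 analytes at d = 0.42 (two-sided alpha 0.05), 10 at d = 0.46 (0.025) or 7 at d = 0.50 (0.0125). The two figures do not identify their inputs.

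**2. Which stratum differences matter.** Let D = log2(post) − log2(control) within subject. A stratum shift in level enters both terms and cancels. In a simulation of 10/10/10 strata, level shifts of 0, 1 and 3 units between adjacent strata left the unadjusted standard error at 0.181 and power at 0.81, with no gain from adjustment (0.81). Only stratum differences in D remain.

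**3. Assumptions for the size.** Two-sided 5%, a single contrast, n = 30 with 10 per stratum, and total variance of D equal to 1. R² is the share of that variance lying between strata. It is not in the documents; the range 0 to 0.30 is assumed. Setting unadjusted power to 82% at 29 df gives noncentrality 2.975, so d = 2.975/√30 = 0.543.

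**4. Adjusted test.** The error variance becomes 1 − R² on 27 df, so the noncentrality is 2.975/√(1 − R²):
- R² = 0: 2.975, power 81.8%
- R² = 0.10: 2.975/√0.90 = 3.136, power 85.6%
- R² = 0.20: 2.975/√0.80 = 3.326, power 89.4%
- R² = 0.30: 2.975/√0.70 = 3.556, power 92.9%

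**5. Unadjusted test under the same fixed strata.** The true standard error of the mean is √((1 − R²)/30), but the test estimates about √(((1 − R²) + R² × 30/29)/30). At R² = 0.20 these are √(0.80/30) = 0.163 and √(1.007/30) = 0.183. Simulation with equally spaced stratum means (200,000 runs per scenario) gives:

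| R² | Unadjusted power | Adjusted power | Gain (points) | Null rejection, unadjusted | Null rejection, adjusted |
|---|---|---|---|---|---|
| 0 | 82.0% (exact) | 81.8% | −0.2 | 5.0% | 5.0% |
| 0.10 | 83.1% | 85.6% | 2.5 | 3.9% | 5.0% |
| 0.20 | 84.3% | 89.4% | 5.1 | 2.9% | 4.9% |
| 0.30 | 85.8% | 92.9% | 7.1 | 2.0% | 5.1% |

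**6. Starting from 93%.** With d = 0.649, adjusted power is 92.9%, 95.1%, 96.9% and 98.4% at the same R² values. The gain is at most 2.1, 3.9 and 5.4 points over 93%, and less in fact, because the unadjusted test's own power also rises.

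**7. What these R² values mean.** For equally spaced stratum means (−c, 0, +c) around the overall mean, R² = 2c²/3, so c = √(1.5R²): 0.387, 0.548 and 0.671 at R² = 0.10, 0.20 and 0.30. With an overall mean of 0.543, the least responsive stratum averages 0.156, about 0 and −0.128. Under this pattern, R² of 0.20 or more means one stratum shows no average activation at all.

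**8. Break-even.** Adjustment narrows the confidence interval once R² exceeds about 0.006.

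**The case against.** The strongest objection is that section 8.1 is a sample-size paragraph that names no model. A reader might infer that the sponsor decided to pool the strata and ignore them; the text shows only silence. That stands. What can be said is that no SD term is written in, and that the choice is open.

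A reader might also infer that the plan expects activation to rise with SD level, so that precision is certainly being lost. The endpoint says only that a correlation will be assessed, and no stratum effect is given anywhere. At R² near 0 nothing is lost.

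A third tempting step is to compare the adjusted figures with a fixed 82%, which suggests gains of about 4, 7 and 11 points. That treats the strata as randomly sampled. With fixed strata the unadjusted test also gains, and the fair differences are about 2.5, 5 and 7 points.

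The anchor is also weak. The 82% is the plan's least favourable case, and both stated figures depend on correlation between analytes, so they describe a pathway-level procedure rather than the single contrast used here.

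Finally, uneven drop-out might be said to bias the pooled mean. Completers of 12/10/8 with stratum means 0.2/0.6/1.0 would give (2.4 + 6.0 + 8.0)/30 = 0.547 against 0.600 for equal weights. These inputs are purely illustrative. The documents do not predict unequal loss, and they define the primary target as SD skin without stating weights. The quotas may serve only to spread SD level for the exploratory correlation. Equal weighting is thus a proposal that matches the planned mix.

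None of this removes the core: the strata are fixed and recorded, and using them costs almost nothing.

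**Conclusion.** The point holds as an optional efficiency improvement. As written, the primary comparison has no SD term, and any stratum differences in log2 fold change would make an unadjusted paired test conservative. On the assumptions in step 3 of the working, adjustment takes power from about 83% to 86%, 84% to 89% and 86% to 93% at R² of 0.10, 0.20 and 0.30, and costs about 0.2 points at R² = 0. From the stated 93% the gains are smaller. R² is unknown, and the upper part of the range implies large stratum differences, so the lower figures may be the more realistic guide.

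A reader might take this as showing that the primary analysis is invalid. It does not: the unadjusted test rejects at or below its nominal level in every scenario examined.

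**What to change.** Add one sentence to section 8.1: log2 fold change at 1 h and at 24 h will be analysed with SD level (mild, moderate, severe) as a fixed factor, and the primary test will be of the average SSL effect over the three strata, equally weighted to match the planned 12/12/12 mix. Report the stratum means from the same model, which also informs the exploratory endpoint. Keep the unadjusted paired test as a sensitivity analysis.

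If a mixed model of log2 levels is preferred, it needs stratum-by-time terms; a stratum main effect alone would not remove differences in fold change.

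Cost: two residual degrees of freedom (29 to 27 with 30 evaluable subjects), about 0.2 power points if SD level is irrelevant, and no new data.

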2.2 Immunohistochemistry

The use of immunohistochemical biomarkers permits studies with smaller sample size and shorter duration compared to studies that use cancer incidence as an endpoint. To be valid, the quantitative degree and pattern of biomarkers should correlate with carcinogenic transformation or alternatively biomarkers markers may demonstrate the effect of a particular agent on a molecular pathway or biochemical processes (i.e. arachadonic acid/cyclooxygenase pathways, polyamine synthesis). This has been demonstrated by the suppression of polyamine levels in tissue treated with the polyamine synthesis inhibitor, alpha-2-(Difluoromethyl)-dl-ornithine, or DFMO [20,21].

In a previous study completed by this group, IHC was performed on samples collected at baseline, 5 min, and 1, 5, and 24 h following 2X MED of SSL on SP skin of 10 subjects; there was a significant increase in pTOPK and pPRPK activity starting as early as 5 min post SSL exposure with a sustained expression up to 24 h (**Fig. 1**). Analysis of TLR4 using the same samples also revealed increased pathway activation primarily at 24 h post-SLL exposure.

IHC assays will include pTLR4, MyD88, p-p65/NFKB, TAB2, pTOPK, p-PRPK, p-Erk, pP38, and pP90RSK. IHC assays previously established will also be performed for validation of SSL-induced changes.

[figure not shown]

Fig. 1. Comparison of p-PRPK and p-TOPK levels on sUV-exposed human skin harvested in a time-dependent manner. IHC staining was performed and representative data analyzed (30 photos from 10 subjects) for each of the following: normal human skin without sUV, 5 min post 2X MED sUV, 1 h post 2 MED sUV, 5 h post 2 MED sUV and 24 h post 2 MED sUV. Shown is expression of phosphorylated (p)-PRPK (a) and p-TOPK (b). Magnification: 400x. **Upper panels:** Phosphorylated PRPK, total and p-TOPK levels are presented as sum of the integrated optical density (IOD) values. **Lower panels:** Representative staining (brown color) is shown. The asterisks (*, **) indicate a significant difference ($p < 0.05$ or $p < 0.001$, respectively).

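### Is the rule for choosing one post-exposure time point per pathway too loosely defined to be used?

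*Combined protocol and SAP*

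**What the plan says.** Section 1.0 (Objectives) gives the purpose: "We will also determine the optimal time points for evaluation of biomarker modulation". It also says how the answer will be used: "The results of this study will be used to aid in design of pharmacodynamic SSL exposure studies" with small molecule inhibitors. Section 6.2 fixes the candidates: "Skin punch biopsies will then be collected at 1 hour (± 15 minutes) and 24 hours (± 2 hours) post-SSL exposure", with an unexposed control from the same forearm.

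The selection rule is in Section 8.1: "the most appropriate post-SSL time point (per pathway) will be selected based on the combination with the largest effect sizes". The lead-in to that sentence is "Exploratory analyses will associate the SD score/severity level with analyte activation in the SD samples. Based on these analyses". The rule then appears again in a run-together sentence: "an exploratory systems biology analysis will be conducted based on these analyses, one post-SSL time point (per pathway) will be selected for future studies", with the same criterion, "will be selected for future studies based on the combination with the largest effect sizes".

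Section 8.1 describes the primary analysis as a comparison of RPPA analytes at baseline with those at 1 h or 24 h. It mentions the log2 fold change once, in the power statement. It gives no effect-size formula, analyte list, combining rule or interval for the choice of time. Section 2.2 lists nine IHC markers without assigning them to pathways.

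**The concern.** Three things look open. *Effect size* could be a mean log2 fold change or a change divided by its SD. *Combination* could be the single strongest analyte at a given time or all analytes of the pathway taken together. And because the first statement of the rule follows the sun-damage association and the second follows the systems biology analysis, the effect in question could even be read as something other than the change after SSL.

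If these readings picked different times, the choice could be settled after the data are seen, and a near tie could be passed on as a clear winner. The group's earlier data make a near tie conceivable for TOPK. In sun-protected skin of 10 subjects, Section 2.2 reports a rise in "pTOPK and pPRPK activity starting as early as 5 min post SSL exposure with a sustained expression up to 24 h". TLR4 rose mainly at 24 h, so it is less exposed.

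**Working it through.** **The plan's own figures.** 36 × 0.85 = 30.6, which agrees with the 30 evaluable subjects in Section 8.1. That section states power for the primary comparison (93% or above, and 82%) but no figure for the time-point choice, so there is nothing to reproduce for it. Those power figures cannot be rebuilt either, because test, alpha, effect size and number of analytes are not given. The point here does not depend on them.

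**Inputs.** From Section 8.1: n = 30 and within-pathway correlation ρ from 0 to 0.6. Assumed: m = 4-5 analytes per pathway, between-time correlation r = 0.5, and a true standardised change of 0.5 at 1 h.

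**How well a fixed rule separates the times.** For the mean over m analytes with SD 1:

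- V = (1 + (m − 1)ρ)/m
- SE of the paired 24 h minus 1 h difference = √(2(1 − r)V/n)
- P(pick the better time) = Φ(gap/SE)

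With m = 5:

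| ρ | V | SE | 95% half-width (2.045 × SE) | P at gap 0.2 | P at gap 0.5 |
|---|---|---|---|---|---|
| 0.4 | 2.6/5 = 0.52 | √(0.52/30) = 0.132 | 0.27 | Φ(1.52) = 0.94 | above 0.99 |
| 0.6 | 3.4/5 = 0.68 | √(0.68/30) = 0.151 | 0.31 | Φ(1.33) = 0.91 | above 0.99 |

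Simulation with the SD estimated gives 89-92% at a gap of 0.2 for the mean standardised effect, slightly lower as expected.

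**How often readings disagree** (simulation, m = 4-5, ρ = 0 to 0.6):

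| Readings compared | Times equal | 24 h better by 0.2 SD | 24 h better by 0.5 SD |
|---|---|---|---|
| Largest single analyte v mean standardised effect, equal SDs | 14-27% | 8-12% | under 1% |
| Mean standardised effect v mean log2 fold change, SD at 24 h 1.2 times that at 1 h | 23-36% | 1.5-10% | at most 0.3% |

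In the second row, *equal* means equal standardised effects. The fold changes then differ (0.5 × 1.2 = 0.60 against 0.50), so the two scales ask different questions. At an SD ratio of 1.3 the disagreement is 30-44%, again at that exact tie.

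**What a disagreement costs.** With a uniform gap of 0.2 SD and m = 5 (ρ = 0.4 to 0.6), averaging is wrong in 8-11% of trials, an average loss of 0.2 × 0.08 = 0.016 to 0.2 × 0.11 = 0.022 SD. The largest-analyte reading is wrong in 14-15%, a loss of 0.028 to 0.030 SD. The two differ by about 0.01 SD.

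**Where the readings really part.** If only one analyte in five is better at 24 h, by 0.5 SD, averaging is right in 73-76% of trials and the largest analyte in 91-93%. With a uniform gap of 0.2 SD the order reverses: 89-92% against 85-86%. With nine analytes, take 0.6 for all at 1 h, and 1.5 for one and 0.3 for eight at 24 h. The 24 h mean is then (1.5 + 8 × 0.3)/9 = 0.43, below 0.6. The largest-analyte reading picks 24 h in 98-100% of trials and mean log2 fold change in 0-13%. Likewise, means of 0.8 v 0.6 with SDs of 1.3 v 0.8 (24 h v 1 h) give standardised effects of 0.62 v 0.75. Mean log2 fold change then picks 24 h in 88-100% of trials and the mean standardised effect in 4-21%.

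**Which analysis the rule refers to.** The aim in Section 1.0 is modulation of biomarkers by SSL, and the primary analysis is the change from baseline. Choosing a time by its association with sun damage would not serve that aim. The systems biology reading arises only where the same instruction has been pasted twice and run into its neighbour.

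**The case for a change.** The strongest case for a change is that the time point is a main product of the study, the rule's terms are undefined, and the last pair of examples shows opposite answers almost every time. A few sentences would remove the freedom to choose a reading after the data are seen, at no cost in samples. A paired 24 h minus 1 h difference with its interval would show whether the winner was clear.

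The textual part of this stands: the definitions are not written down. The numerical part is weaker. The largest rates in the disagreement table come from exact ties and shrink quickly once one time is better in every analyte. The opposite-answer examples need a lone dominant analyte or a marked SD contrast, which the documents neither support nor exclude. In those cases the readings measure different things, and no reading is shown to be wrong.

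The interval would be useful reporting, but it would not alter the choice. At a 0.2 SD gap it would cover zero in 69-75% of trials and a time would still be picked. Since Section 8.1 analyses both times against baseline, the data for that comparison will exist, and nothing says that only the chosen time will be reported. Quoting the winner's effect without comment would overstate it somewhat (0.57-0.58 against a true 0.50 when the times are equal), but the plan does not say that a later study will be sized on that number.

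**Conclusion.** No change to the plan is called for. Section 8.1 leaves the effect scale and the combining rule unstated, but the rule can be applied and its object is clear from the stated aim. The choice is not a confirmatory test, so no error rate is affected. Its result will aid the design of later studies.

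Under the assumed inputs, the two ways of combining analytes disagree in about 8-12% of trials at a uniform 0.2 SD advantage and in under 1% at 0.5 SD. The choice between them is worth about 0.01 SD in the former case. Where they diverge more, averaging and the largest analyte each win in a different setting, so fixing one is a trade-off and not a correction. The repeated sentence is a clerical slip.

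These sizes rest on assumed analyte counts, effects, SDs and between-time correlation, none of which the documents give. A marked difference in variability between 1 h and 24 h, or a single dominant analyte, would make the reading matter more. An analyst would see either from the results at both times.
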